##### **5.1.3.3 Antibodies Against Components of UB-313**

Antibody titers against components of UB-313 (include but are not limited to anti-CGRP target epitope, anti-UBITH, and anti-CpG1) will be summarized.

#### 5.1.3.4 Cytokine Release included by UB-313

#### 5.2 Cytokine release from peripheral blood mononuclear cell (PBMC)s stimulated with component of UB-313 (T-cell ELISpot) will be summarized. Safety Analyses

Safety will be assessed by Adverse Events (AEs), Adverse Event of Special Interests (AESIs), medically attended adverse events (MAAEs), local (injection site) and systemic (generalized) reactions (i.e., reactogenicity), clinical laboratory assessments, vital signs, physical neurological and examinations and electrocardiograms (ECGs), through the end of study. Safety analysis will be based on safety analysis set.

#### 5.2.1 Extent of Exposure

The number of injections and total dosage of study drug will be summarized.

#### 5.2.2 Treatment Tolerability

Overall treatment tolerability will be summarized in the safety population.

The overall treatment tolerability of UB-313 for each dose group is defined as the percentage of number of administered doses divided by number of administered doses plus number of missed doses of participant(s) who drops out due to drug-related AE(s). It is calculated according to the following formula:

$$100\% \times (A+B1+C+D) / (A+B1+B2+C+D)$$

where

A: number of administered doses of completers

B1: number of administered doses of participant(s) who drops out due to drug-related AE(s)

B2: number of missed doses of participant(s) who drops out due to drug-related AE(s)

C: number of administered doses of participant(s) who drops out due to drug-unrelated AE(s)

D: number of administered doses of participant(s) who drops out not due to AE(s)

## 5.2.3 Adverse Events

Adverse events (AEs) will be coded using MedDRA. The actual version of MedDRA will be noted in the statistical tables and clinical study report. The intensity of the AEs is graded according to the Common Terminology Criteria for Adverse Events (CTCAE), version 5.0.

An AE will be considered a treatment-emergent adverse event (TEAE) if the AE began or worsened (increased in severity or became serious) after the first administration of study drug.

A treatment-emergent serious adverse event (TESAE) is defined as an SAE that is also a TEAE.

TEAEs will be summarized by participant incidence rates. The number and percentage of participants with TEAEs will be tabulated for overall (i.e., any preferred term), as well as by primary MedDRA SOC and PT.

### 5.2.3.1 Adverse Event Overview

An overview of AEs will be presented. The number and percentage of participants experiencing at least one event will be summarized for each of the below categories.

- Treatment related TEAE
- Serious TEAE
- Treatment related serious TEAE
- Adverse events of special interest (AESI)

AESI is defined in Protocol Appendix 4 ADVERSE EVENTS OF INTEREST.

AESI MedDRA terms based on Protocol Table 5 AESIs based on identified adverse reactions and Table 6 AESIs based on important potential risks are listed in Appendix 2.

- Medically attended adverse event (MAAE)
- Death

### 5.2.3.2 Treatment-Emergent Adverse Events

The number and percentage of participants will be tabulated for the below categories of TEAEs.

- TEAEs by SOC and PT
- TEAEs by SOC, PT and maximum severity

- TEAEs by SOC, PT and maximum relationship
- Treatment-related TEAEs by SOC and PT
- SAEs (including deaths) by SOC and PT
- TEAEs leading to treatment discontinuation by SOC and PT
- AESIs by SOC and PT
- MAAEs by SOC and PT

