### **4.0 General Consideration**

All analyses will be conducted using observed data only and no missing data will be imputed.

In general, the baseline value is defined as the last available value before the first injection of study dose.

All analysis and summary will be performed by dose group, defined as below:

- 100/100/100 $\mu$ g (8 active participants in cohort 1)
- 300/100/100 $\mu$ g (8 active participants in cohort 2)

- 300/300/300 $\mu$ g (8 active participants in cohort 3)
- 600/100/100 $\mu$ g (8 active participants in cohort 4)
- Placebo (8 participants from all cohorts)

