### 5.2.3.3                   Solicited Adverse Events

Solicited local and systemic AEs are defined in protocol section 7.5.3.2 Reactogenicity Assessment, and protocol appendix 3: Toxicity grading scale for solicited adverse events.

Local (injection site) and systemic (generalized) reactions (i.e., reactogenicity) after each study product injection will be presented by maximum severity. Summary will include counts and percentages of participants by dose group for each reaction and each injection.

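### Unsolicited TEAEs, related TEAEs and AESIs are tabulated only cumulatively from the first injection, with no split by injection, although three of the four regimens differ in dose only at injection 1

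*SAP*

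**What the plan says.** SAP 4.0 fixes the reporting unit: "All analysis and summary will be performed by dose group, defined as below". The groups are the four complete three-injection regimens (100/100/100, 300/100/100, 300/300/300 and 600/100/100 µg, 8 active participants each) and 8 pooled placebo participants.

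SAP 5.2.3 opens the treatment-emergent window at the first injection. It gives no end to the window and no link to the most recent injection. It then states "TEAEs will be summarized by participant incidence rates".

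SAP 5.2.3.1 gives an overview of participants with at least one event, by category. SAP 5.2.3.2 adds the SOC and PT tables: "The number and percentage of participants will be tabulated for the below categories of TEAEs". These include TEAEs, treatment-related TEAEs and AESIs. None is divided by injection or period.

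SAP 5.2.3.3 treats solicited reactions differently: "Summary will include counts and percentages of participants by dose group for each reaction and each injection".

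Two other places bear on the point. SAP 2.2 plans a Week 16 end-of-treatment analysis that covers all safety data, and a separate end-of-study analysis. The Protocol's Schedule of Assessments (footnote 3) has AEs recorded from consent through follow-up or early termination. The last visit is Week 44.

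**The concern.** Safety and tolerability is a primary objective, and the Protocol synopsis escalates on the first dose: 100, then 300, then 600 µg. After injection 1, cohorts 1, 2 and 4 receive the same doses. Any difference in the dose given among these three therefore lies in the interval from Day 1 to Day 29.

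The planned tables count a participant once from the first injection onward. An unsolicited event on Day 10 after 600 µg and one in Week 40, 28 weeks after a 100 µg injection, fall in the same 600/100/100 cell. Two things are lost. Where background events are common, participants who would have had an event anyway mask those whose event followed the first dose. And even where background is low, the table cannot show which injection an event followed.

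**Working it through.** **Plan's own figure.** There is none to reproduce. The documents give no AE rates, effect size or power, and plan no formal test of AEs.

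**Inputs from the Schedule of Assessments.** Injections are on Days 1, 29 and 85. Week 16 is Day 113 and Week 44 is Day 309.

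- Injection 1 to injection 2: 29 − 1 = 28 days, which is 28/308 = 9% of follow-up (309 − 1 = 308 days).
- Extra time after Day 29 in the Week 16 cut: (113 − 29)/7 = 12 weeks.
- Extra time after Day 29 in the end-of-study cut: (309 − 29)/7 = 40 weeks.
- Follow-up after injection 3: (309 − 85)/7 = 32 weeks.

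**Assumptions, not in the documents.** The background hazard of a first event is constant, with 44-week risk p. Injection 1 adds an independent risk a = 0.30 of an event before Day 29.

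**Formulas.** With t days since injection 1:

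- Background risk by day t: B(t) = 1 − (1 − p)^(t/308).
- Risk with the added effect: 1 − (1 − B(t))(1 − a).
- Difference: a × (1 − p)^(t/308).

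The ratio of two windows depends only on p and not on a.

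**At p = 0.75:**

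- 28 days: B = 1 − 0.25^(28/308) = 0.118, against 1 − 0.882 × 0.70 = 0.383. Difference 26.4 points.
- Week 16 (112 days): B = 1 − 0.25^(112/308) = 0.396, against 1 − 0.604 × 0.70 = 0.577. Difference 18.1 points.
- Week 44: 0.750 against 1 − 0.25 × 0.70 = 0.825. Difference 7.5 points.

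Per 8 participants these are 2.1, 1.4 and 0.6 extra participants with an event.

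**Over a range of backgrounds (a = 0.30, differences in points):**

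| 44-week background | 28 days | Week 16 | Week 44 | 28 days ÷ Week 16 | 28 days ÷ Week 44 |
|---|---|---|---|---|---|
| 5% | 29.9 | 29.4 | 28.5 | 1.01 | 1.05 |
| 10% | 29.7 | 28.9 | 27.0 | 1.03 | 1.10 |
| 50% | 28.2 | 23.3 | 15.0 | 1.2 | 1.9 |
| 75% | 26.4 | 18.1 | 7.5 | 1.5 | 3.5 |
| 90% | 24.3 | 13.0 | 3.0 | 1.9 | 8.1 |

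The upper rows stand for single, uncommon preferred terms. The lower rows stand for any TEAE or a common term.

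**A second set of assumptions.** With a background of 2% per week and 50% added risk, the difference is 0.46 at 4 weeks, 0.36 at 16 weeks and 0.21 at 44 weeks. The pattern is the same.

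**The case against.** A reader might infer that these events are tabulated only once, over the whole study, so that 40 further weeks of background swamp every AE table. The documents do not support that.

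- **Two cuts.** The Week 16 analysis in SAP 2.2 covers all safety data and adds 12 weeks, not 40. At an assumed 75% background it recovers (18.1 − 7.5)/(26.4 − 7.5) = 56% of the loss. It still merges all three injections. SAP 2.2 also mentions pooling by dose without defining it, and that does not supply a split by injection.
- **Most rows are SOC or PT rows.** At 5% to 10% background the dilution is close to nil.
- **Related TEAEs** are already filtered by causality, so background events judged unrelated do not enter. What remains is the mixing of injections.
- **AESIs.** Of the 31 terms in SAP Appendix 2, 8 are injection-site terms and probably overlap the solicited reactions already shown per injection. The solicited list is in protocol sections not available here. Terms such as constipation, alopecia, hypersensitivity and muscle spasms are not injection-site terms.
- **Delayed effects.** This is an active immunotherapy. The synopsis expects maximal responses to be assessed at Week 16 and studies duration to Week 44, so a larger first dose may act beyond Day 29. The objective concerns regimens, and tabulation by regimen suits it. This objection stands: later intervals should not be labelled by the latest dose alone, and the cumulative tables must remain.
- **Safety review.** The Safety Review Committee looks at data after 1 week of observation. That serves escalation and is not a reported analysis.
- **Sparse counts.** With 8 per group, many interval cells will hold very few events. That is a real cost.

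Table shells were not available, so a by-injection display cannot be excluded. If one exists, the SAP text should say so.

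**Conclusion.** The point holds in a limited form. The SAP text plans no display of unsolicited TEAEs, related TEAEs or AESIs by injection, at either cut, although dose differs only at injection 1 for three of the four regimens and the SAP already uses that split for solicited reactions.

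The dilution matters for the any-TEAE row and common terms: by a factor of 3.5 at end of study and 1.5 at Week 16, if background is 75% over 44 weeks. It is small for rare terms. For related TEAEs, what is lost is mainly the ability to see which injection an event followed. All rates are assumed, and the model places the whole first-dose effect before Day 29. An effect that persists longer would be diluted less. This is a worthwhile addition to the safety reporting and does not invalidate the planned tables.

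**What to change.** Keep the cumulative tables. In SAP 5.2.3.2, add TEAE, treatment-related TEAE and AESI tables by onset interval:

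1. injection 1 to before injection 2;
2. injection 2 to before injection 3;
3. injection 3 to Week 16;
4. Week 16 to Week 44.

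The first three apply at the end-of-treatment analysis and all four at end of study. Specify the following:

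- **Denominator:** participants who received that injection and were followed in the interval. For interval 4, the injection is injection 3. Events in participants who missed an injection remain in the cumulative tables.
- **Columns:** by regimen, with the dose given at that injection shown. Pool by dose only in interval 1, where cohorts 2 and 3 both received 300 µg (16 active participants).
- **Footnote:** intervals describe timing and do not attribute cause, since immune effects of an earlier dose may persist.

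The cost is programming from onset and injection dates, which the TEAE definition already relies on. No new data or tests are needed. The downside is more tables, many with sparse counts.

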### 5.2.3.3                   Solicited Adverse Events

Solicited local and systemic AEs are defined in protocol section 7.5.3.2 Reactogenicity Assessment, and protocol appendix 3: Toxicity grading scale for solicited adverse events.

Local (injection site) and systemic (generalized) reactions (i.e., reactogenicity) after each study product injection will be presented by maximum severity. Summary will include counts and percentages of participants by dose group for each reaction and each injection.

### 5.2.4                   Laboratory Data

#### 5.2.4.1                   Hematology and Chemistry Parameters

Clinical laboratory values will be reported in International System of Units (SI) units and categorized based on normal ranges collected from laboratories.

Summary and plot will be presented.

The number and percentage of participants who experienced laboratory test abnormalities will be summarized for each lab assay.

For each scheduled postbaseline visit, shift from baseline will be presented based on the categories below:

- Low, Clinically Significant
- Low, Not Clinically Significant
- Normal
- High, Not Clinically Significant
- High, Clinically Significant

Unscheduled visits will be presented in listings but will not be included in summaries.

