Endpoints	
Primary Endpoints
 
Safety will be assessed by adverse events (AEs), adverse events of special interest (AESIs), medically attended adverse events (MAAEs), local (injection site) and systemic (generalized) reactions (i.e., reactogenicity), clinical laboratory assessments (e.g., chemistry, hematology, urinalysis), vital signs, neurological and physical examinations, and electrocardiograms (ECGs) through the end of study.
 
Immunogenicity will be measured by serum anti-CGRP antibody titers and analyzed from baseline to Week 16 and through the end of study (Week 44).
 
Secondary Outcome Measure/Endpoints
 
Pharmacodynamics (PD) of the immune response will be measured by the inhibition of capsaicin-induced increase in DBF and analyzed from baseline to Week 16 and either until return to baseline or until Week 44, whichever comes first.
 
Exploratory Outcome Measures/Endpoints
 
Exploratory outcome measures may include but are not limited to the following:
 
 • CGRP concentrations in serum through the end of study. • Antibody titers against components of UB-313 (i.e., CpG1 and UBITh1) through the end of study. • Isotype-specific anti-CGRP antibody titers through the end of study. • Cytokine release from peripheral blood mononuclear cells stimulated with a component of UB-313 (T-cell ELISpot) through Week 16.

Methodology	
This single center, double-blind, placebo-controlled, multidose regimen, first-in-human (FIH) study of UB-313, an anti-CGRP peptide -based immunotherapeutic candidate, is designed to assess the safety, tolerability, and immunogenicity of 4 selected UB-313 dose regimens in healthy adults.
																																										
	
Screening Period
																																										
	
All participants will undergo Laser Speckle Contrast Imaging (LSCI) assessments at Screening to ensure a capsaicin response of at least 100% increase in DBF.
																																										
	
Following Screening, all eligible participants (approximately 40) will be randomized to receive 3 IM injections of UB-313 or placebo in a staggered manner by cohort as described below.
																																										
	
Investigational Product Dosage and Schedule:
																																										

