Statistical Considerations	
As this is an FIH study, the sample size is based on the exploratory nature of the design. No statistical power to be considered to determine the sample size.
 
Primary time-points for immunogenicity and PD are two-fold:
 
a) First phase at the end of Week 16 for evaluating maximal immuno-responses elicited by the 4 dosage regimens (i.e., cohorts) of UB-313
 
b) Second phase of response maintenance period after Week 16 until the end of study (Week 44), in which effects of the 4 dosage regimens of UB-313 on the duration of responses will be evaluated.
 
When any cohort completes Week 16, first phase analyses can be conducted based on cleaned cohort data up to Week 16. To maintain blinding for the remainder of the study, the first phase analyses will be conducted and reviewed only by a designated and independent team before the end of study final database lock. The purpose of the early analyses of first phase data prior to the completion of the study is to have an early read out of the first part of the primary immunogenicity and PD results to refine the development plan. Design of the second phase of the study will not be changed based on results from the first phase data.

Table 1: Study Schedule of Assessments

The Investigator may perform visits outside of the scheduled study visits (unscheduled visits) listed in the Schedule of Assessments table to conduct evaluations or assessments required to protect the well-being of the participant.

Visit Number ¹	Screen ²	V1 ^{2,5}		V1a ⁵	V1b ⁵	V2	V3 ⁵		V3a ⁵	V3b ⁵	V4	V5	V6 ⁵		V6a ⁵	V6b ⁵	V7	V8	V9, V10, V11	V12/ET
Week	Up to 4 wks	W0				W1	W4				W5	W8	W12				W13	W16	W20, W28, W36	W44
Day (Visit Window)	-28 to -1	D1 (-3D)	D1 --	D2	D3	D8 ($\pm 3D$)	D29 (-3D)	D29 ($\pm 3D$)	D30	D31	D36 ($\pm 3D$)	D57 ($\pm 5D$)	D85 (-3D)	D85 ($\pm 3D$)	D86	D87	D92 ($\pm 3D$)	D113 ($\pm 7D$)	D141, D197, D253 ($\pm 14D$)	D309 ($\pm 14D$)
Visit Type	SRN	Pre IMP	IMP	CRU	TC	CRU	Pre IMP	IMP	CRU	TC	CRU	CRU	Pre IMP	IMP	CRU	TC	CRU	EoT CRU	CRU	EoS/ET CRU
General Assessments and Procedures																				
Informed consent	X																			
Demographic	X																			
Medical history	X																			
Eligibility assessment	X	X																		
Medication review	X	X	X	X	X	X	X	X	X	X	X	X	X	X	X	X	X	X	X	
AE/SAE review ³	X	X	X	X	X	X	X	X	X	X	X	X	X	X	X	X	X	X	X	
Investigational Medicinal Product Administration and Assessments																				
Randomization		X																		

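### Hematology and chemistry: the rule that keeps unscheduled visits out of summaries makes no exception for the count of participants with an abnormality, so that count can be too low

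*SAP*

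**What the plan says.** Three statements in SAP section 5.2.4.1 (Hematology and Chemistry Parameters) matter here, in this order.

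- A participant-level count: "The number and percentage of participants who experienced laboratory test abnormalities will be summarized for each lab assay". It is not tied to any visit.
- A shift table, restricted by its own words: "For each scheduled postbaseline visit, shift from baseline will be presented based on the categories below".
- A closing rule: "Unscheduled visits will be presented in listings but will not be included in summaries".

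The introduction to the protocol's Table 1 (Study Schedule of Assessments) lets the investigator hold visits outside the schedule "to conduct evaluations or assessments required to protect the well-being of the participant". The protocol synopsis lists "clinical laboratory assessments (e.g., chemistry, hematology, urinalysis), vital signs, neurological and physical examinations" among the components of the primary safety endpoint, followed through the end of the study. SAP section 4.0 sets the reporting groups: "8 active participants in cohort 1", the same number in each of the other three active groups, and 8 placebo participants pooled across cohorts.

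**The concern.** Leaving unscheduled results out of by-visit means, plots and by-visit shift tables is ordinary practice, because such results belong to no planned time point. A count of participants who ever had an abnormality is a different kind of statistic. It asks whether an abnormal value was seen at any time, and an unscheduled result answers that as well as a scheduled one. If the closing rule is applied to this count, the table can show no abnormality for a participant whose abnormal result is in the trial database and in the listings.

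At stake is the accuracy of one tabulated part of the primary safety endpoint in a first-in-human study. With groups of 8, the difference between no participant and one participant is visible to any reader of the table.

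**Working it through.** The documents give no figure to reproduce. The check is a reading of the rule, followed by simple arithmetic.

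**1. Does the exclusion reach the count?** The shift table is already limited to scheduled visits, so the closing rule adds nothing there. Its effect must fall on the other summaries in the section: the descriptive summary and plot, and the participant count. The count is itself described as something to be summarized, and no exception is stated. On the plain wording it is covered.

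**2. Who is affected?** For one assay and one participant:

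| Abnormal at a scheduled visit | Abnormal at an unscheduled visit | Counted, rule as written | Counted, all post-baseline values |
|---|---|---|---|
| No | No | No | No |
| Yes | No | Yes | Yes |
| Yes | Yes | Yes | Yes |
| No | Yes | **No** | **Yes** |

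Only the last row differs, and always in the same direction. With the denominator unchanged (assumed to be the dose group in the Safety Analysis Set), the rule lowers the count or leaves it as it is.

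**3. Can the last row occur?** As the schedule table reads after extraction, chemistry and hematology are drawn on Days 1, 8, 29, 36, 57, 85, 113, 141, 197, 253 and 309, which gives 10 post-baseline draws. Gaps between successive draws:

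- 8 − 1 = 7, 29 − 8 = 21, 36 − 29 = 7, 57 − 36 = 21 days
- 85 − 57 = 28, 113 − 85 = 28, 141 − 113 = 28 days
- 197 − 141 = 56, 253 − 197 = 56, 309 − 253 = 56 days

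After the first and second injections (Days 1 and 29) the next draw comes 7 days later; after the third (Day 85) it comes 28 days later. A change that arises and resolves inside a gap would be missed by the scheduled draws and could be seen only at an unscheduled one. The visit columns were read from a PDF and should be checked against the original.

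**4. Size per participant.** One participant in a group of 8 is 1/8 = 12.5 percentage points; in the 4 × 8 = 32 active participants pooled it is 1/32 = 3.1 points. Exact (Clopper-Pearson) 95% intervals are 0 to 36.9% for 0/8 and 0.3 to 52.7% for 1/8. They overlap widely, and the SAP plans no interval for laboratory rates. The issue is a correct count, not a changed inference.

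**5. Frequency.** Let q be the share of participants whose only abnormal value for an assay is unscheduled. The documents do not give q. The chance that a group of 8 has at least one such participant is 1 − (1 − q)^8. As pure assumptions:

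- q = 5%: 1 − 0.95^8 = 34%
- q = 10%: 1 − 0.90^8 = 57%
- q = 20%: 1 − 0.80^8 = 83%

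The chance falls towards zero as q does. Nothing in the documents selects a value, and the conclusion does not depend on one.

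**The case against.** The strongest reply is that the closing rule directly follows the shift categories, which are introduced for scheduled visits, and may have been meant only to complete that by-visit rule. That may well be the intention. The wording does not say so, however, and a programmer who follows it would drop unscheduled values from the count too. The text needs the clarification on either reading.

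A second reply is that nothing is lost. The values are listed, which is manageable with about 40 participants. Adverse events, including medically attended ones, are tabulated with no exclusion of unscheduled visits. The Safety Review Committee reviews the available safety data before escalation. All of this stands, and it limits the harm. It does not correct the tabulated percentage: a listing leaves the table unchanged, and an adverse-event table is a different measure from classification against laboratory normal ranges. How far adverse-event reporting would pick up such values cannot be judged, because the protocol text available here ends with the notes to Table 1.

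A third reply is that unscheduled values have a drawback of their own: a participant sampled more often has more chances of an out-of-range result. This is true and belongs in a table footnote. It does not justify recording an observed abnormality as absent.

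A reader might also infer more than the documents support:

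- **That all laboratory summaries are affected.** The rule stands only in the hematology and chemistry section. SAP 5.2.4.2 (urinalysis, inflammatory markers, cytokines) does not repeat it.
- **That the omitted values are the ones most likely to be abnormal.** The protocol gives participant well-being as the purpose of these visits. It does not say that blood is drawn at each, and it gives no abnormality rate. Some draws may be repeats in participants already counted.
- **That late transient changes are visible only at unscheduled draws.** A transient change can coincide with a scheduled draw.
- **That the rule favours the active product.** It applies equally to placebo, and no differential effect is shown.
- **That ECG has the same fault.** SAP 5.2.4.6 plans a shift to the worst post-baseline value and states no exclusion of unscheduled readings.

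**Conclusion.** The point holds for the hematology and chemistry participant count in SAP 5.2.4.1. As written, the exclusion covers that count, and its effect can only be to understate the count or leave it unchanged. The size is 12.5 percentage points for each affected participant in a group of 8; how many would be affected is unknown. The conclusion rests on the plain wording of the section and on a denominator that does not change with the rule. It does not rest on any assumed frequency of unscheduled abnormal results, and it does not claim bias between groups or a risk to participants during the study. The count belongs to the primary safety endpoint, and the data needed are already collected and listed, so the SAP should be corrected.

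**What to change.** In SAP 5.2.4.1, limit the exclusion of unscheduled visits to by-visit descriptive statistics, plots and by-visit shift tables. Add that the number and percentage of participants with any post-baseline hematology or chemistry abnormality is based on all post-baseline values, scheduled and unscheduled. A table footnote can say that unscheduled values are included and that the number of samples may differ between participants. No ECG change is needed.

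The cost is one sentence in the SAP and a minor programming change. Reported abnormality rates may be slightly less favourable, and they will depend to some extent on how often each participant was sampled.
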